3.1 General Design

This is a phase II, single arm, unblinded trial of about 12 months of consolidation Pembrolizumab after proton reirradiation with or without concurrent chemotherapy for isolated local and regional thoracic recurrences of NSCLC. Forty-one patients will be treated with re-irradiation with or without standard concurrent chemotherapy to all gross disease with proton beam therapy. The intended radiation dose should be at least 60 Gy of reirradiation in 1.8-2.0 Gy fractions with or without concurrent chemotherapy or in 4.0 Gy fractions without chemotherapy, at the provider's discretion. This corresponds to daily fractionated radiation over a period of approximately 3-8 weeks. Four to 12 weeks after completing reirradiation, patients will begin Pembrolizumab consolidation. Pembrolizumab will be given at a fixed dose of 200 mg intravenously approximately every 21 days for 17 cycles (about 12 months) if there is no evidence of progressive disease or intolerable side effects.

Subjects will be evaluated approximately 30 days prior to consolidation Pembrolizumab and every 12 weeks (1 day after until the day of the next infusion) while on Pembrolizumab with radiographic imaging to assess disease status. If new signs or symptoms of progression occur between scheduled scans, directed imaging will be obtained at the clinically appropriate time point to document disease status. Investigators will make all treatment-based decisions using RECIST 1.1. Adverse events will be monitored upon initiation of Pembrolizumab treatment and continue throughout the trial and graded in severity according to the National Cancer Institute (NCI) CTCAE version 5.0. For the

Phase II Pembrolizumab Reirradiation

Pembrolizumab phase, all treatment-related toxicities will be recorded.

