7 TRIAL FLOW CHART

7.1 Trial Flow Chart

Table 6: Study procedures by visit

Trial Period:	Screening Phase	Proton Reirradiation +/- Chemo-therapy	Pembrolizumab Treatment Cycles*										Post-Treatment	
Treatment Cycle /Title:	Screening	Reirradiation	1/9	2/10	3/11	4/12	5/13	6/14	7/15	8/16	17	Safety Follow-up	Follow Up Visits	
Scheduling Window (Days):	-28 to -1	Daily protons for 3-8 weeks	± 3	± 3	± 3	± 3	± 3	± 3	± 3	± 3	At last treatment	30 days post tx/discon	Every 3 months for 2 yrs	
Administrative Procedures														
Informed Consent	X													
Inclusion/Exclusion Criteria	X													
Demographics and Medical History	X													
Prior and Concomitant Medication Review	X	X	X	X	X	X	X	X	X	X	X			
Trial Treatment Administration			X	X	X	X	X	X	X	X	X			
Post-study anticancer therapy status												X		X
Survival Status		X	X	X	X	X	X	X	X	X	X	X		X
Clinical Procedures/Assessments														
Review Adverse Events**			X	X	X	X	X	X	X	X	X	X		X
Full Physical Examination	X					X				X		X		X
Directed Physical Examination		X	X	X	X		X	X	X		X			
Vital Signs and Weight	X	X	X	X	X	X	X	X	X	X	X	X		X
ECOG Performance Status	X	X	X	X	X	X	X	X	X	X	X	X		X
Laboratory Procedures/Assessments: analysis performed by LOCAL laboratory														
Pregnancy Test – Urine or Serum β-HCG	X													
PT/INR and aPTT	X													
CBC with Differential	X			X	X	X	X	X	X	X	X	X		X
Comprehensive Serum Chemistry	X			X	X	X	X	X	X	X	X	X		X

Phase II Pembrolizumab Reirradiation

Trial Period:	Screening Phase	Proton Reirradiation +/- Chemo-therapy	Pembrolizumab Treatment Cycles*										Post-Treatment	
			Pembrolizumab Treatment Cycles*										Post-Treatment	
Treatment Cycle /Title:	Screening	Reirradiation	1/9	2/10	3/11	4/12	5/13	6/14	7/15	8/16	17		Safety Follow-up	Follow Up Visits
Scheduling Window (Days):	-28 to -1	Daily protons for 3-8 weeks	± 3	± 3	± 3	± 3	± 3	± 3	± 3	± 3	At last treatment	30 days post tx/discon	Every 3 months for 2 yrs	
Urinalysis	X				X				X			X		
T3, FT4 and TSH	X			X			X			X		X		
Efficacy Measurements														
Tumor Imaging	X***	X	X				X, X				X			X
Tumor Biopsies/Archival Tissue Collection/Correlative Blood Studies														
Archival or Newly Obtained Tissue Collection (optional)	X													
Correlative Studies Blood Collection	X			X				X			X	X	X	

For the Pembrolizumab phase, we will report all treatment-related toxicities.

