8.1.2 Clinical Procedures/Assessments

8.1.2.1 Adverse Event (AE) Monitoring

The investigator or qualified designee will assess each subject to evaluate for potential new or worsening AEs as specified in the Trial Flow Chart and more frequently if clinically indicated. Adverse experiences will be graded and recorded after the start of Pembrolizumab and during the follow-up period according to NCI CTCAE Version 5.0. Toxicities will be characterized in terms regarding seriousness, causality, toxicity grading, and action taken with regard to trial treatment.

All AEs of unknown etiology associated with Pembrolizumab exposure should be evaluated to determine if it is possibly an event of clinical interest (ECI) of a potentially immunologic etiology (irAE). See Section 5.7.1.1 and the irAE guidance document (attached Appendix) regarding the identification, evaluation and management of AEs of a potential immunological etiology.

Please refer to section 8.2 for detailed information regarding the assessment and recording of AEs.

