8.2 Assessing and Recording Adverse Events

An adverse event is defined as any untoward medical occurrence in a patient or clinical investigation subject administered a pharmaceutical product and which does not necessarily have to have a causal relationship with this treatment. An adverse event can therefore be any unfavorable and unintended sign (including an abnormal laboratory finding, for example), symptom, or disease temporally associated with the use of a medicinal product or protocol-specified procedure, whether or not considered related to the medicinal product or protocol-specified procedure. Any worsening (i.e., any clinically significant adverse change in frequency and/or intensity) of a preexisting condition that is temporally associated with the use of the Merck's product, is also an adverse event.

Merck product includes any pharmaceutical product, biological product, device, diagnostic agent or protocol-specified procedure, whether investigational (including placebo or active comparator medication) or marketed, manufactured by, licensed by, provided by or distributed by Merck for human use.

Phase II Pembrolizumab Reirradiation

Adverse events may occur during the course of the use of Merck product in clinical trials or within the follow-up period specified by the protocol, or prescribed in clinical practice, from overdose (whether accidental or intentional), from abuse and from withdrawal.

All adverse events will be recorded from beginning with cycle 1 of Pembrolizumab through 30 days following cessation of treatment and at each examination on the Adverse Event case report forms/worksheets. Laboratory AE's will also start being recorded beginning with cycle 1 of Pembrolizumab. The reporting timeframe for adverse events meeting any serious criteria is described in section 8.2.3.1.

Applicable reporting to DSMC will occur as follows:

On-Site subjects (this includes any subjects enrolled at other sites on an in-house study)

1. All grade 3 or higher events (AE or SAE) within five business days of knowledge.
2. All unexpected deaths within 24 hours of knowledge.
3. All others deaths within 30 days of knowledge. Deaths of subjects off-study for greater than 30 days from the last study treatment/intervention are not reportable with the following exceptions:

Study Exceptions the CTSRMC will not Approve:

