9.3.1 Analysis Endpoints

Primary

Progression Free Survival (PFS) per RECIST 1.1

Progression Free Survival is defined as the time from initiation of definitive therapy to the first documented disease progression per RECIST 1.1 based on radiologists' review or death due to any cause, whichever occurs first, or last patient follow-up that documented lack of disease progression. Patients who have not had disease progression or who have died, will be censored on the most recent clinical evaluation date that documented that they were progression-free.

Secondary

Overall Survival

Overall Survival (OS) is defined as the time from initiation of definitive therapy to death due to any cause or last patient contact alive. Subjects without documented death at the time of the final analysis will be censored at the date of the last follow-up.

Toxicity Determination

Tolerability of therapy will be determined on the basis of CTCAE adverse event reporting. Toxicity will be reported separately for definitive therapy and Pembrolizumab. For the definitive therapy phase, we will report on adverse events which are grade 3 or higher treatment-related toxicities or any grade of pneumonitis or esophagitis. For the Pembrolizumab phase, we will report all treatment-related toxicities.

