9.4 Statistical Methods

Primary Objective

1. The primary intent-to-treat analysis will estimate progression free survival from initiation of definitive therapy by the Kaplan-Meier method. Median PFS and 95% CI will be determined. A total of 41 patients will be enrolled on the study.
2. A secondary proof of principle analysis will determine the clinical benefit of adding consolidation Pembrolizumab after definitive therapy. Only patients who receive consolidation Pembrolizumab are included in this analysis. It is expected that up to 15% of enrolled patients will have progressive disease or lingering toxicity and will not start Pembrolizumab after definitive therapy. Thus we anticipate that at least 35 patients will be included.

In this proof of principle analysis, we will compare progression free survival from initiation of definitive therapy to a historical control value. We assume the median PFS for the historical control population treated with standard therapy only is 6 months and the median PFS for the patients treated with definitive therapy and consolidation Pembrolizumab is 10 months. Assuming 35 patients are enrolled over 2 years and followed for an additional 3 months, the final analysis will have 80% power to detect an improvement in median PFS assuming exponential survival and 1-sided 5% significance level.

Secondary Objectives

1. Overall survival will be estimated by the Kaplan-Meier method. Median OS and 95% CI will be determined.
2. Toxicities will be graded, categorized and tabled. For the definitive therapy phase, we will report on adverse events which are grade 3 or higher treatment-related toxicities or any grade of pneumonitis or esophagitis. For the Pembrolizumab phase, we will report all treatment-related toxicities.

Exploratory Objective

1. Biomarkers will be tested for association with PFS using log rank test for categorical biomarkers and Cox proportional hazards regression for continuous biomarkers. Biomarkers will be tested for association with graded toxicity (i.e., worse toxicity grade) for specific categories of toxicity using chi square test for categorical biomarkers and Spearman's correlation for continuous biomarkers.

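### A separate toxicity report is promised for the reirradiation phase, but adverse event recording starts at pembrolizumab cycle 1, 7 to 20 weeks after the first fraction, so that report is likely to be incomplete.

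*Combined protocol and SAP*

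**What the plan says.** **What is to be reported.** Toxicity is a secondary endpoint (section 3.3). Section 9.3.1 states: "Toxicity will be reported separately for definitive therapy and Pembrolizumab". It then sets the content of the first part: "For the definitive therapy phase, we will report on adverse events which are grade 3 or higher treatment-related toxicities or any grade of pneumonitis", with esophagitis added in the same sentence. Section 9.4 repeats this and says that toxicities will be graded and tabulated.

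**When recording starts.** Four places give the same start:

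- Section 3.1: "Adverse events will be monitored upon initiation of Pembrolizumab treatment and continue throughout the trial".
- Section 8.1.2.1: "Adverse experiences will be graded and recorded after the start of Pembrolizumab".
- Section 8.2: "All adverse events will be recorded from beginning with cycle 1 of Pembrolizumab through 30 days following cessation of treatment". It adds that laboratory adverse events "will also start being recorded beginning with cycle 1 of Pembrolizumab".
- Flow chart, section 7.1: the row "Review Adverse Events" is empty under Reirradiation and has its first mark at cycle 1. Directed examination, vital signs and ECOG status are marked under Reirradiation.

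**Who may not reach cycle 1.** Section 9.4 expects that "up to 15% of enrolled patients will have progressive disease or lingering toxicity and will not start Pembrolizumab".

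**The concern.** The plan promises an output but does not set up the data collection that would feed it. Pneumonitis and esophagitis of any grade are named as results to be reported for the reirradiation phase, yet the rules for monitoring, grading and recording begin only after that phase is over.

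Section 1.1 explains why this matters: toxicity has limited the use of thoracic reirradiation, and protons are proposed partly to reduce it. If mild and moderate events that come and go before cycle 1 are not collected, the regimen may look better tolerated than it is, and a reader of the results would have no means of judging by how much.

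**Working it through.** **1. Length of the interval before recording starts.** Inputs, both from section 3.1: reirradiation lasts about 3 to 8 weeks, and pembrolizumab begins 4 to 12 weeks after it ends.

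- Shortest: 3 + 4 = 7 weeks from first fraction to cycle 1.
- Longest: 8 + 12 = 20 weeks.

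The reirradiation duration agrees with the stated fractionation. Assuming five fractions a week, 60 Gy in 4.0 Gy fractions is 15 fractions, or 3.0 weeks. In 2.0 Gy fractions it is 30 fractions, or 6.0 weeks. In 1.8 Gy fractions it is 34 fractions, or 6.8 weeks. Since 60 Gy is given as a minimum, an upper end near 8 weeks is plausible.

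**2. The plan's own count of patients starting pembrolizumab.** 41 x (1 - 0.15) = 34.85, which rounds to the stated 35. That leaves 41 - 35 = 6 expected non-starters. The 15% is a planning expectation, with progression and toxicity combined. It is not a cap on non-starters or on lost events.

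**3. Is there another route into the definitive-phase report?**

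| Provision | What it captures | What it leaves out |
|---|---|---|
| 4.4.1, 4.4.2 | Reason for stopping on the CRF; follow-up of patients stopped for toxicity until it resolves or stabilizes | Patients who go on to cycle 1 |
| 8.1.5.3 | A check for symptomatic grade 3+ pneumonitis before pembrolizumab | An entry condition, not a recording rule; lower grades |
| 8.1.4.1, 8.1.5.6 | Safety visit; all events before it to be recorded | No start date; visit timed from the last dose of trial treatment |
| 8.2, DSMC reporting | Events of grade 3 or higher | No stated start; grades 1-2 |
| 8.2.3.2 | Some events of clinical interest from consent onward | The listed events are overdose and a combined liver-test criterion |
| 8.1, 8.1.2.6, 8.1.3.1 | Standard-of-care records, scans and blood tests | No required grading or transfer to a study form |

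Events still present at cycle 1 could also be picked up then. None of these routes systematically captures grade 1-2 pneumonitis or esophagitis that begins and resolves before cycle 1.

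**4. Attribution.** The grade 3+ category is limited to treatment-related events. The causality scale for the adverse event form (section 8.2.4, Table 8) asks only about the supplied drug, and its negative answer covers a subject who has not received that drug. An event caused by reirradiation or chemotherapy before cycle 1 therefore has no attribution rule on the form. Pneumonitis and esophagitis of any grade carry no relatedness condition in section 9.3.1, so this gap does not touch them.

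**5. Population.** Section 9.2 counts as evaluable anyone who receives at least one dose of reirradiation. Section 9.3.3 builds the safety population on *study treatment* without saying whether reirradiation counts. Section 8.2.3.1 defines an SAE by use of the supplied drug and gives no date on which capture starts.

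**The case against.** The best case for the plan is that the start at pembrolizumab is deliberate. A flow-chart footnote treats the therapy that follows baseline imaging as standard of care, section 8.1.3.1 leaves blood tests in that phase to standard of care, and section 8.1 places standard-of-care procedures outside the protocol. Section 2 words the toxicity objective around pembrolizumab, as does section 3.4. On this view the definitive-phase data would come from clinical records at a single center, and section 9.4 does commit to grading and tabulating them. The IRB reporting text in section 8.2 also has a relatedness test wider than the drug.

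Much of this stands. The commitment to grade exists; what is missing is the operational step, meaning a visit, a form and a start date. Charts could recover part of the information. But nothing names charts as the source, and they hold only what was noted and can be graded. The IRB test governs prompt reporting, not the adverse event form.

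A reader might infer that reirradiation toxicity would go wholly unrecorded, or that non-starters would vanish selectively from the safety data. The documents do not support either. The partial sources above are real, and patients stopped for toxicity must be followed to resolution or stabilization. For non-starters, coverage is ambiguous rather than absent.

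**Conclusion.** The point holds as an internal inconsistency. Followed as written, the start rule in sections 3.1, 7.1, 8.1.2.1 and 8.2 leaves the definitive-phase report in sections 9.3.1 and 9.4 without systematic data for 7 to 20 weeks per patient. The clearest loss is grade 1-2 pneumonitis and esophagitis that resolves before cycle 1. The reported rates are likely to be biased low, because unrecorded events can only reduce the count. This rests on two assumptions: that sites follow the stated start, and that charts are not systematically abstracted.

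The number of events missed, and so the size of the bias, cannot be computed from the documents. The 15% expectation should not be read as a bound on it.

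The consequence is limited. The report is descriptive, with no hypothesis or decision rule attached, and the primary PFS analysis is unaffected.

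A minor separate item is the post-treatment window for patients who complete 17 cycles. The flow-chart footnote gives one year of adverse event monitoring, while sections 5.8 and 8.2 give 30 days. A reader might take this as a flat contradiction. Section 3.1 makes 30 days a floor, which reconciles it in part, but the wording should still be aligned.

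**What to change.** 1. Reconcile sections 3.1, 7.1, 8.1.2.1 and 8.2 with 9.3.1 and 9.4. Grade and record only the categories already named in 9.3.1, with attribution to reirradiation or chemotherapy, from the first fraction to cycle 1, or to a stated end date for patients who never start pembrolizumab. Use the existing reirradiation visits plus a look-back entry at the pre-pembrolizumab screening (8.1.5.3), since the flow chart has no column for the gap. For patients already past this phase, abstract from charts and label those data retrospective.
2. State in section 8.2.3.1 when SAE capture starts.
3. Report definitive-phase toxicity on the evaluable set of section 9.2, and state in 9.3.3 whether *study treatment* includes reirradiation.
4. Separately, align the post-treatment window for completers across section 3.1, section 5.8, the flow-chart footnote and section 8.2.

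The cost is a protocol amendment, a short toxicity form with modest data entry, and chart abstraction for every patient already treated, potentially up to 41. These are data-capture changes only; clinical management is not touched.

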8.1.5.3 Pre-Pembrolizumab Screening

Visit requirements are outlined in Section 7.0 - Trial Flow Chart.

Subjects will be eligible to move on to pembrolizumab treatment cycles if they received at least 50 Gy of reirradiation, if they have no progressive disease on tumor imaging, and if they do not have symptomatic CTCAEv5 grade ≥ 3 pneumonitis.

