Seriousness	
A serious adverse event is any adverse event occurring at any dose or during any use of Merck product that:
 
†Results in death; or
 
†Is life threatening; or places the subject, in the view of the investigator, at immediate risk of death from the event as it occurred (Note: This does not include an adverse event that, had it occurred in a more severe form, might have caused death.); or
 
†Results in a persistent or significant disability/incapacity (substantial disruption of one's ability to conduct normal life functions); or
 
†Results in or prolongs an existing inpatient hospitalization (hospitalization is defined as an inpatient admission, regardless of length of stay, even if the hospitalization is a precautionary measure for continued observation. (Note: Hospitalization [including hospitalization for an elective procedure] for a preexisting condition which has not worsened does not constitute a serious adverse event.); or
 
†Is a congenital anomaly/birth defect (in offspring of subject taking the product regardless of time to diagnosis); or
 
Is a new cancer; (that is not a condition of the study) or
 
Is an overdose (whether accidental or intentional). Any adverse event associated with an overdose is considered a serious adverse event. An overdose that is not associated with an adverse event is considered a non-serious event of clinical interest and must be reported within 24 hours.
 
Other important medical events that may not result in death, not be life threatening, or not require hospitalization may be considered a serious adverse event when, based upon appropriate medical judgment, the event may jeopardize the subject and may require medical or surgical intervention to prevent one of the outcomes listed previously (designated above by a †).
	
Duration	
Record the start and stop dates of the adverse event. If less than 1 day, indicate the appropriate length of time and units
	
Action taken	
Did the adverse event cause the Merck product to be discontinued?
	

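### Adverse-event recording starts at pembrolizumab cycle 1, yet the plan promises a toxicity report for the reirradiation phase that precedes it

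*Combined protocol and SAP*

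**What the plan says.** Three sections place the start of adverse-event work at pembrolizumab.

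- Section 3.1: "Adverse events will be monitored upon initiation of Pembrolizumab treatment and continue throughout the trial".
- Section 8.1.2.1: "Adverse experiences will be graded and recorded after the start of Pembrolizumab and during the follow-up period".
- Section 8.2: "All adverse events will be recorded from beginning with cycle 1 of Pembrolizumab through 30 days following cessation of treatment". It sets the same start for laboratory events.

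Table 6 matches them. Its adverse-event review row has no mark under Screening or Reirradiation and begins at cycle 1, although directed examination, vital signs and ECOG status are marked under Reirradiation.

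The statistical section assumes that earlier data exist. Section 9.3.1 says: "Toxicity will be reported separately for definitive therapy and Pembrolizumab". For the definitive phase, "we will report on adverse events which are grade 3 or higher treatment-related toxicities or any grade of pneumonitis or esophagitis". Section 9.4 repeats that commitment under the secondary objectives.

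Not every patient reaches cycle 1. Section 9.4 expects that "up to 15% of enrolled patients will have progressive disease or lingering toxicity and will not start Pembrolizumab". Section 8.1.5.3 sets the gate: "Subjects will be eligible to move on to pembrolizumab treatment cycles if they received at least 50 Gy of reirradiation", and only if imaging shows no progression and there is no symptomatic grade 3 or higher pneumonitis.

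**The concern.** A stated recording rule conflicts with a stated secondary endpoint. The events promised for the definitive phase mostly arise before the point at which the protocol begins to record events.

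The missing information is unlikely to be a random sample. Patients held back from pembrolizumab by toxicity never reach the start of recording, and a mild event that has cleared by cycle 1 need not leave an entry.

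This matters because section 9.3 says the study evaluates the whole multi-stage plan, and section 1.1 describes radiation in this setting as carrying high toxicity risk. A reader of the results will take the definitive-phase table as the safety record of reirradiation.

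**Working it through.** **1. Time before recording opens.** Section 5.2 gives about 3-8 weeks of reirradiation and a start of pembrolizumab 4-12 weeks after it ends.

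- Shortest: 3 + 4 = 7 weeks.
- Longest: 8 + 12 = 20 weeks.

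**2. Patients who never reach cycle 1.** Section 9.4 gives 41 enrolled and up to 15% not starting.

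- Starters: 41 × (1 − 0.15) = 34.85, which reproduces the plan's figure of 35.
- Non-starters: 0.15 × 41 = 6.15, or 41 − 35 = 6. These include patients who progress as well as those with toxicity, and the plan does not give the split.

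**3. What else could capture the promised events.**

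| Provision | What it catches | What it leaves |
|---|---|---|
| DSMC notice of grade 3 or higher events (8.2) | Severe events the team learns of, with no phase limit | Grade 1-2 pneumonitis and esophagitis; no visit or stated start for seeking events |
| Pneumonitis check before pembrolizumab (8.1.5.3) | Symptomatic grade 3 or higher pneumonitis at one time point | Lower grades, esophagitis, events already resolved |
| Discontinuation reason on the CRF and follow-up of toxicity (4.4.1, 4.4.2) | Toxicity that ends participation | Toxicity that does not |
| Handling of events at discontinuation (8.1.4.1) | Events present at that time | Events that came and went |
| Safety Follow-Up Visit (8.1.5.6) | All events before the visit, with no start date | Timed from the last dose of trial treatment, which Table 6 marks only from cycle 1, so its reach to non-starters is unclear |
| Events of clinical interest from consent (8.2.3.2) | Overdose and one liver-test pattern, under conditions | The promised categories |

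Serious-event reporting does not close the gap. Section 8.2.3.1 gives no collection start, and the definition is tied to the drug: "A serious adverse event is any adverse event occurring at any dose or during any use of Merck product that".

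**4. Attribution.** Table 8 asks only whether the Merck product caused the event. An event before the first dose falls under its negative answer. Pneumonitis and esophagitis are reportable at any grade without attribution, so they are not affected. Other grade 3 or higher events must be treatment-related to count, and there is no field for relationship to radiation or chemotherapy.

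**5. Denominator.** Section 9.3.3 requires one dose of study treatment, a term it does not define. Sections 5.9 and 9.2 count a patient from one proton dose, which gives 41. Table 6 marks trial treatment from cycle 1, which gives about 35. One affected patient is then 1/41 = 2.4% or 1/35 = 2.9%.

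**The case against.** The strongest reply is that reirradiation is background care. A Table 6 footnote calls it standard-of-care treatment, section 8.1.3.1 leaves its blood tests to standard of care, and section 8.1 puts standard-of-care procedures outside the protocol. A restricted report abstracted from charts may be what was intended. The CRFs, the data-management procedures mentioned in section 10.6 and the DSMC monitoring plan are not in the documents. Section 1.1 also reports acceptable toxicity in an initial proton cohort with low target volumes.

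Much of this stands. It rules out any claim that nothing would be known about the definitive phase. It does not supply a form, a visit or a start date for the promised events, and chart abstraction is nowhere specified.

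A reader might also infer three stronger things, none of which the documents support.

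- **That severe pneumonitis would vanish from the report.** The check in 8.1.5.3, the discontinuation reason in 4.4.1 and the DSMC notice would all have to be ignored.
- **That the shortfall can be put as a rate.** This needs the true number of events, the share still present at cycle 1, the share of non-starters with toxicity, and the yield of the partial routes above. The documents give none of them.
- **That events in the 4-12 week rest period belong to neither report.** Section 9.3.1 sets no cut-off on onset, so a radiation-related event during the rest can be reported as definitive-therapy toxicity.

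**Conclusion.** The inconsistency is real and should be corrected. For about 7-20 weeks per patient, and for up to about 6 of 41 patients throughout, the protocol requires no prospective record of the events that 9.3.1 and 9.4 promise to report.

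The clearest losses are:

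- grade 1-2 pneumonitis and esophagitis that resolve before cycle 1;
- attribution of other grade 3 or higher events to radiation or chemotherapy;
- events in patients who never start pembrolizumab.

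The likely direction is understatement, since unrecorded events can only lower the count. Its size cannot be estimated from the documents. The conclusion assumes that the protocol is followed as written and that no form or procedure outside these documents fills the gap. Toxicity is a secondary endpoint; the PFS analysis and the sample size do not depend on this point.

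**What to change.** 1. In 3.1, 8.1.2.1, 8.2 and the Reirradiation column of Table 6, require the 9.3.1 event categories to be recorded from the first proton fraction to the first pembrolizumab dose. If pembrolizumab is not started, record them to 12 weeks after the last fraction, by chart review or existing contacts. State that this period is the definitive-phase report.
2. In Table 8, add relationship to reirradiation and relationship to chemotherapy beside relationship to the Merck product.
3. In 9.3.3, set two denominators: patients with at least 1 proton fraction for the definitive phase, and patients with at least 1 pembrolizumab dose for the pembrolizumab phase.

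The cost is one amendment, two extra fields and modest data entry. Reirradiation visits already include examination, vital signs and ECOG status, so event review can be added there. The extra tracking of non-starters concerns up to about 6 patients. Patients already treated would need chart abstraction, which will recover mild events less completely than prospective recording.
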